8.2. Image Acquisition

Central imaging core lab readers will independently assess all PyL PET/CT images as well as any subsequent conventional images performed following PyL PET/CT.

8.2.1. Follow-up conventional imaging to verify PyL-suspected lesion(s) within 60 days following ¹⁸F-DCFPyL PET/CT

Within 60 days following ¹⁸F-DCFPyL PET/CT imaging, if a positive lesion(s) is identified on ¹⁸F-DCFPyL PET/CT and tissue acquisition of the PyL-suspected lesion is not feasible, then conventional imaging (e.g., targeted MRI or CT, fluciclovine or choline PET) will be performed in an attempt to anatomically correlate the PyL-suspected lesion(s). All follow-up imaging will be sent to the central imaging core lab. The choice of the most appropriate conventional imaging modality will be at the discretion of the investigator; use of the most sensitive imaging method is encouraged, such as targeted MRI for verification of the PyL-suspected bone lesion(s).

If tissue acquisition (by surgery or biopsy) of the PyL-suspected lesion is feasible, then see [Section 8.4 Histopathology](#).

8.2.2. ¹⁸F-DCFPyL PET/CT Imaging

Prior to enrollment, all PET/CT scanners to be used in this study must be qualified in accordance with the procedures outlined in the [Imaging Manual](#).

¹⁸F-DCFPyL PET/CT imaging will be performed using local PET/CT scanners with low dose CT for attenuation correction and anatomic localization as described in the [Imaging Manual](#). Subjects will be asked to void prior to imaging. After voiding, a whole-body CT and PET scan will be acquired starting from the mid-thigh through the skull. Whole body PET/CT scans must be obtained within 60-120 minutes following the ¹⁸F-DCFPyL dosing.

All ¹⁸F-DCFPyL PET emission data should be acquired and reconstructed in accordance with the [Imaging Manual](#).

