10.4.2.1. Primary Endpoint Analysis

The primary endpoint of the CLR is evaluated in a subset of FAS subjects with at least one positive lesion identified by PyL PET/CT imaging (per local interpretation). The CLR at the subject-level is defined as the percentage of subjects for whom there is a one-to-one correspondence between localization of at least one lesion identified on ¹⁸F-DCFPyL PET/CT imaging and the composite truth standard.

The composite truth standard is defined in [Section 8.1](#).

The CLR is computed as $100 \times TP / (TP + FP)$; TP = true positives, FP = false positives.

A true positive (TP) result is defined as a subject with both a positive lesion(s) on ¹⁸F-DCFPyL PET/CT and a positive result on the composite truth standard:

- Positive finding for prostate cancer of a PyL-suspected lesion according to local histopathology (one confirmed anatomical correlate will suffice to declare the PyL PET/CT a true positive), or
- Positive finding for prostate cancer of a PyL-suspected lesion upon follow-up conventional imaging performed following PyL PET/CT (one confirmed anatomical correlate will suffice to declare the PyL PET/CT a true positive), or
- PSA decreases drop by $\geq 50\%$ from baseline following RT without concomitant ADT up to 9 months following initiation of such treatment.

False positives will be defined as subjects with positive lesion(s) on PyL PET/CT who have the following negative findings for prostate cancer according to the composite truth standard:

- Negative finding for prostate cancer of a PyL-suspected lesion according to local histopathology, or
- Negative finding for all PyL positive lesion(s) upon follow-up conventional imaging performed following PyL PET/CT (one confirmed anatomical correlate will suffice to declare the PyL PET/CT a true positive), or
- PSA does not drop by $\geq 50\%$ from baseline following RT (without concomitant ADT) up to 9 months following initiation of such treatment.

The two-sided 95% CI for the CLR will be computed using the normal approximation to the binomial distribution. This analysis will be performed for each of the central imaging core lab

readers. If the lower bound of the 95% CI is >0.2 for two of the three independent imaging reviewers, then the primary endpoint analysis is deemed a success.

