5.1.1. Primary Endpoint

The primary endpoint of the CLR is evaluated in a subset of Full Analysis Set (FAS) subjects with at least one positive lesion identified by ¹⁸F-DCPyL PET/CT imaging by the local reader and then evaluated against the composite truth standard by three independent, blinded central imaging readers. The CLR at the subject level is defined as the percentage of subjects for whom there is a one-to-one correspondence between localization of at least one lesion identified on ¹⁸F-DCFPyL PET/CT imaging (by central review) and the composite truth standard, which is defined either as:

- 1) evaluable local histopathology result for prostate cancer from surgery or biopsy performed within 60 days following PyL PET/CT, or
- 2) if evaluable histopathology is not available, informative conventional imaging (e.g., ¹⁸F-fluciclovine PET (preferred if was not performed at baseline) or choline PET; targeted MRI or CT; fluciclovine or choline PET) finding(s) of the anatomical correlate to the PyL-suspected lesion(s) within 60 days following PyL PET/CT, before locoregional or systemic treatment in is started, or
- 3) if neither of the above is available or informative, confirmed PSA response (PSA decline by ≥50% from baseline, confirmed within 4 weeks per central lab evaluation) post-RT (no concomitant ADT) that was initiated within 60 days following PyL PET/CT. PSA will be collected every 3 months, up to 9 months until PSA response (if achieved) is confirmed.

The CLR in percent is computed as $100 \times TP/(TP+FP)$; TP = true positives, FP = false positives.

A true positive (TP) result is defined as a subject with both a positive lesion(s) on ¹⁸F-DCFPyL PET/CT evaluated by at least one central reader and a positive result on the composite truth standard in the following order of importance:

- Positive finding for prostate cancer of a PyL-suspected lesion according to local histopathology (confirmed by at least one anatomical correlate will suffice to declare the PyL PET/CT assessed by the central reader defining a true positive), or
- Positive finding for prostate cancer of a PyL-suspected lesion upon follow-up correlative imaging by CT, MRI, whole body bone scan, NaF, fluciclovine or choline PET/CT

performed following PyL PET/CT (one confirmed anatomical correlate will suffice to declare the PyL PET/CT assessed by the central reader a true positive), or

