• PSA decreases by ≥50% from baseline following RT (without concomitant ADT) up to nine months following initiation of such treatment if the other two truth standards were not performed or did not provide evaluable results

False positives will be defined as subjects with positive lesion(s) on PyL PET/CT from at least one central reader who has the following negative findings for prostate cancer according to the composite truth standard:

- Negative finding for prostate cancer of a PyL-suspected lesion according to local histopathology, or
- Negative finding for all PyL positive lesion(s) upon follow-up correlative imaging performed following PyL PET/CT, or
- PSA does not decrease by ≥50% from baseline following RT (without concomitant ADT) up to 9 months following initiation of such treatment.

The CLR lesion location(s) will be matched with the CLR lesion location(s) identified by the composite truth standard to determine if colocalization is successful, denoting a true positive (TP) assessment. If a subject has more than one lesion identified by pathology or by correlative imaging, then at least one lesion must be successfully colocalized for the subject to be considered a TP. The anatomic regions and CLR lesion locations matched by laterality (right or left) where applicable are presented in Table 3. The pelvic lymph nodes are grouped together for analysis in alignment with the data collected in the PyL-2301 (OSPREY) study. Within the prostatic region and extra-pelvic lymph nodes, specific CLR lesion location groupings are further modified specific for PET/CT findings based on Prostate Cancer Molecular Imaging Standardized Evaluation (PROMISE)² intended to guide reproducibility, general applicability and clinical relevance.

Table 3: Lesion Locations and Anatomic Regions

Anatomic Region	CLR Lesion Locations
Prostatic	Prostate gland or prostate bed (including seminal vesicles)
Pelvic Lymph Nodes	 Right Pelvic (including Internal Iliac [Hypogastric], External Iliac, Common Iliac, Obturator) Left Pelvic (including Internal Iliac [Hypogastric], External Iliac, Common Iliac, Obturator) Other pelvic (including Rectal/perirectal and Presacral)

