Surgical pathology	Positive	Yes	TP
Surgical pathology	Positive	No	FP
Surgical pathology	Negative	Yes or No	FP

Progenics Pharmaceuticals, Inc. Statistical Analysis Plan: Protocol PyL3301

Composite Truth	Truth Standard	Central PyL	Subject Outcome
Standard Source	Location Result	Reader Location	~ u~jeet e ueeeme
		Match	
Surgical pathology	Unevaluable	Yes or No	Unevaluable, evaluate
			with another truth
			standard
Image guided biopsy,	Positive pathology	Yes	TP
needle or tissue	in the same		
sampling device in PyL	anatomic region as		
positive lesion	at least one PyL		
	positive lesion		
Image guided biopsy,	Negative pathology	Yes	FP
needle or tissue	in the same		
sampling device in PyL	anatomic region as		
positive lesion	at least one PyL		
* '1 11'	positive lesion	**	** 1 11 1
Image guided biopsy,	Positive or negative	Yes or No	Unevaluable, evaluate
needle or tissue	pathology in the		with another truth
sampling device not in	same anatomic		standard
PyL positive lesion	region as at least one		
	PyL positive lesion	271.	
Image guided biopsy,	Positive or negative	N/A	Unevaluable, evaluate
sampling method	pathology in the		with another truth
confirmation is not	same anatomic		standard
applicable or the	region as at least one		
confirmatory image is	PyL positive lesion		
unevaluable	C 1.: T :	3 7	TD
Correlative imaging	Correlative Imaging	Yes	TP
(Truth Panel assessment)	result positive	N.	ED
Correlative imaging	Correlative Imaging	No	FP
(Truth Panel assessment)	result positive	Vac	FP
Correlative imaging	Correlative Imaging	Yes	ГГ
(Truth Panel assessment)	result negative	Yes or No	Unavaluable avaluate
Correlative imaging (Truth Panel assessment)	Correlative Imaging unevaluable	i es oi no	Unevaluable, evaluate with another truth
(Truth Faller assessment)	unevaluable		standard
PSA response following	Observed ≥ 50%	N/A	Unevaluable
locoregional RT	decrease from	1N/A	Officialitable
locoregional K1	baseline up to 9		
	months from start of		
	RT, but response not		
	confirmed		
PSA response following	Radiation therapy	N/A	Unevaluable
locoregional RT	not directed to all	1 1/ / 1	Onevaluable
100010gioilai Ki	PyL suspected		
	lesions		
	10310113		

Statistical Analysis Plan: Protocol PyL3301

Composite Truth	Truth Standard	Central PyL	Subject Outcome
Standard Source	Location Result	Reader Location	
		Match	
PSA response following	Confirmed $\geq 50\%$	N/A	TP
locoregional RT	decrease from		
	baseline at or before		
	9 months from start		
	of RT		

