7. SAMPLE SIZE

7.1. Sample Size Justification and Calculation

The primary endpoint is the correct localization rate (CLR) at the subject level, in subjects with positive PyL PET/CT findings, defined as the percentage of subjects a one-to-one correspondence between localization of at least one lesion identified on ¹⁸F-DCFPyL PET/CT imaging and the composite truth standard. The composite truth standard is defined in Section 5.1.1

The assumed CLR of ¹⁸F-DCFPyL PET/CT imaging is 30%. Based on the varied published experience with ⁶⁸Ga-PSMA PET/CT and a meta-analysis by Perera *et al*³, approximately 76% (95% confidence interval [CI], 66-85%) of PSMA scans are positive in patients with suspected recurrence of prostate cancer following initial therapy. Therefore, in subjects with negative or equivocal findings for prostate cancer on baseline conventional imaging, 60% of subjects are conservatively estimated to have PyL PET/CT positive findings. In consideration of the extent literature for ⁶⁸Ga-PSMA PET and the present study entry criteria, approximately 30% of PSMA PET/CT positive findings may be verified by biopsy/surgery-based histopathology, conventional imaging, or PSA follow-up post-RT.⁴⁻⁷ It is therefore assumed that 30% of the positive PyL results in the study will be confirmed by the composite truth standard. If 60% of the study subjects have positive PyL scans, and 30% of these positive diagnostic scans are confirmed by the composite truth standard, the use of the PyL PET/CT will permit the detection/localization of recurrent prostate cancer in approximately 18% of the underlying target population, versus at most 5% that could be identified by conventional imaging alone.

The sample size estimates are based on the positive likelihood ratio (PLR) of CLR to prevalence.

The PLR is estimated as
$$PLR = \left(\frac{CLR}{1-CLR}\right) / \left(\frac{prevalence}{1-prevalence}\right)$$
.

Conservatively assuming the initial prevalence rate as a population parameter to be 5% by conventional imaging, ^{8,9} ⁴ if a CLR of 30% is realized, the positive likelihood ratio is expected to be 8.1, implying a considerable increase in the clinical value of PyL PET/CT to identify prostate cancer.

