Using a lower bound for the 95% CI for CLR of 20%, the corresponding lower bound for PLR would be 4.75 based on a normal approximation to the Binomial. This will thus require a total of 81 positive PyL scans, which translates to a total of 134 PyL PET/CT scans or evaluable subjects needed. Accounting for a 30% non-evaluable (including loss to follow-up) rate, approximately 192 subjects will need to undergo PyL PET/CT in the study.

During study enrollment, the rate of positive ¹⁸F-DCFPyL PET/CT scans will be calculated periodically to confirm the assumption of 60%. If the observed rate is lower than expected, the sample size may need to be increased.

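### For men whose follow-up imaging covers only some PyL-positive lesions, the narrative false-positive rule and SAP Table 4 conflict, and the direction of bias in CLR depends on which is applied

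*SAP*

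**What the plan says.** **True positive on imaging.** SAP 5.1.1 states that "one confirmed anatomical correlate will suffice to declare the PyL PET/CT assessed by the central reader a true positive". Protocol 10.4.2.1 has the same one-lesion rule.

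**False positive on imaging, narrative text.** SAP 5.1.1 requires "Negative finding for all PyL positive lesion(s) upon follow-up correlative imaging performed following PyL PET/CT". Protocol 10.4.2.1 requires "Negative finding for all PyL positive lesion(s) upon follow-up conventional imaging performed following PyL PET/CT". It is the only imaging FP rule in the protocol.

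**False positive on imaging, SAP Table 4.** Section 5.1.1 also says that centrally positive subjects are classified according to Table 4. Its imaging rows are:

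| Truth Panel imaging result | Location match with central PyL reader | Outcome |
|---|---|---|
| Positive | Yes | TP |
| Positive | No | FP |
| Negative ("result negative") | Yes | FP |
| Negative | No | no row |
| Unevaluable | Yes or No | try another truth standard |

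Table 4 has a row for radiotherapy that was not directed to all suspected lesions (unevaluable). It has no row for imaging that covered only some of them.

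**Coverage.** The choice of modality is left to the investigator. Protocol 4.3.5.1 and 8.2.1 give targeted MRI or CT as examples alongside fluciclovine and choline PET. Once the core lab finds the scan evaluable, the subject completes the study (protocol 4.1).

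**The concern.** Take a man with two PyL-positive lesions in different fields and a targeted MRI of one of them. If the MRI is positive he is a TP under either rule. If it is negative at a location the central reader marked, Table 4 makes him an FP. The narrative bullet does not, because his second lesion has no negative finding. He is then neither TP nor FP, and he drops out of TP/(TP+FP).

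Under the narrative rule, whether such a man is evaluable depends on his result, and only failures are lost. Under Table 4 he stays in either way. The primary denominator, and possibly the decision on the 20% lower limit, therefore depends on which rule the programmer follows.

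**Working it through.** **1. The plan's own figures.** The success criterion rests on a Wald interval: "The two-sided 95% CI for the CLR will be computed using the normal approximation to the binomial distribution". With an assumed CLR of 0.30 and a target lower limit of 0.20 (SAP 7.1):

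- n = 1.96² × 0.30 × 0.70 / 0.10² = 80.67, so 81 positive scans, as stated.
- 80.67/0.60 = 134.5 (plan: 134); 134/0.70 = 191.4, so 192, as stated.
- Likelihood ratios: (0.30/0.70)/(0.05/0.95) = 8.14 and (0.20/0.80)/(0.05/0.95) = 4.75, as stated.

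The sample size reproduces and this point does not affect it. With 81 evaluable subjects a reader needs at least 25 TPs: 25/81 has a lower limit of 20.8%, 24/81 of 19.7%.

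**2. Model for partial coverage.** Let C be the CLR if every lesion were verified, f the share of subjects only partly imaged, and q the chance that a partly imaged subject's scan is positive. Imaging is treated as the truth standard for everyone.

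- Narrative rule: CLR = [(1−f)C + fq] / [(1−f)C + fq + (1−f)(1−C)]
- Table 4 rule (imaged lesion at a matching location): CLR = (1−f)C + fq

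The documents give neither f nor q. Two cases bracket q when one of two lesions is imaged: lesions fully concordant within a man (q = C), or independent (q = 1 − √(1−C), which is 0.163 at C = 0.30).

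**3. Results at C = 30%.**

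| f (assumed) | Narrative, concordant | Narrative, independent | Table 4, concordant | Table 4, independent |
|---|---|---|---|---|
| 10% | 32.3% | 31.2% | 30.0% | 28.6% |
| 20% | 34.9% | 32.7% | 30.0% | 27.3% |
| 30% | 38.0% | 34.6% | 30.0% | 25.9% |

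Example, f = 20%, concordant, narrative: 0.30/(0.30 + 0.80 × 0.70) = 0.30/0.86 = 34.9%. Independent: (0.24 + 0.0327)/(0.2727 + 0.56) = 32.7%; Table 4 gives 0.2727.

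**4. Effect on the success rule.** Enrolment runs until the evaluable count is reached (protocol 10.4.2), so dropped negatives can be replaced. Holding n at 81 with C = 20%, the probability that one reader reaches 25 TPs is:

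| Case | Narrative | Table 4 |
|---|---|---|
| No partial imaging | 1.35% | 1.35% |
| f = 10%, concordant | 3.55% | 1.35% |
| f = 20%, concordant | 8.94% | 1.35% |
| f = 20%, independent | 4.15% | 0.38% |

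The narrative figures with partial imaging exceed the one-sided 2.5% implied by a two-sided 95% interval. Trial success needs two of three readers; these are one-reader figures.

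**5. A fixed data set near the threshold.** With 24 TPs the Wald lower limits are 19.7% (24/81), 19.96% (24/80) and 20.2% (24/79). Dropping two negatives flips that reader.

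**The case against.** The strongest reply is that Table 4 is the SAP's operative classification and already makes the partly imaged, negative man an FP. That disposes of a stronger reading that a reader might infer, namely that such men can never be FP and that the plan inflates CLR outright. The documents do not support it: inflation arises only if the narrative rule is followed. But Table 4 is in the SAP alone, the protocol has only the narrative rule, and SAP 5.1.1 contains both with no order of precedence.

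Other points on that side:

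- **Any-versus-all is not itself a fault.** For an endpoint of at least one lesion, any positive and all negative are exact complements when every lesion is verified. This is correct. The problem is incomplete verification.
- **The bullet could mean all lesions assessed on that scan.** That reading would agree with Table 4, but the wording does not say it.
- **Partial coverage may be uncommon.** What the protocol encourages is the most sensitive method, with targeted MRI as its example for bone. SAP 5.1.1 prefers fluciclovine PET where it was not done at baseline and also lists whole-body bone scan. This bears on how often the problem occurs, and no frequency is given.
- **A result flip is a knife-edge case.** A reader might infer that 10% partial coverage is enough to change the trial's result. If six negatives leave a set of 81, only 23 or 24 TPs change the outcome: 22/75 still fails (19.0%) and 25/81 already passes. At a CLR of 30% those two counts have about 19% probability for one reader.
- **Sensitivity analyses exist.** SAP 8.4 and 8.5.2.2 plan multiple imputation and a tipping point for unevaluable truth standards. The imputation assumes data missing at random, which fails if men are excluded because their scan was negative. The tipping point can show fragility but cannot say which primary rule applies.
- **The Imaging Review Charter may record coverage.** It was not available, so this is open.

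**Conclusion.** The point holds as a conflict between two stated rules for the primary denominator, one of which makes evaluability depend on the result. Bias is upward under the narrative rule and zero or downward under Table 4. Table 4 is also incomplete: imaging negative with no match has no outcome, although negative surgical pathology is FP whether or not the location matches, and partial imaging coverage is not addressed.

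The size is illustrative. It rests on assumed partial-coverage shares of 10% to 30% and on an assumed relation between imaged and unimaged lesions. On those assumptions a CLR of 30% reads about 31% to 38% under the narrative rule and 26% to 30% under Table 4. The documents do not establish that the planned analysis will overstate CLR, and a changed result is plausible only close to the 20% limit. The conflict should be resolved because it concerns the primary endpoint and can be settled without looking at outcomes.

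**What to change.** Before database lock:

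1. Replace the imaging FP bullet in protocol 10.4.2.1 and SAP 5.1.1 with one outcome-neutral rule that agrees with Table 4. A subject is evaluable by imaging if at least one PyL-positive lesion is covered by evaluable follow-up imaging, and is an FP if no covered lesion is confirmed at a matching location.
2. In Table 4, add the row for imaging negative with no location match, and a row stating how partial coverage is handled.
3. Have the Truth Panel record which PyL locations each follow-up scan covered, unless the Imaging Review Charter already provides for this.
4. Report a sensitivity analysis limited to subjects with all PyL lesions covered, or with partly covered negatives scored both ways (as FP and as unevaluable).

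The cost is wording in two documents and at most one form field. The downside is that a man whose unimaged lesion is real would count as an FP, so CLR may come out slightly lower. The sensitivity analysis would show by how much.

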3. TRIAL ENDPOINTS

3.1. Primary Endpoint

The CLR at the subject level, defined as the percentage of subjects for whom there is a one-to-one correspondence between localization of at least one lesion identified on ¹⁸F-DCFPyL PET/CT imaging and the composite truth standard (See [Section 8.1](#))

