Extra-pelvic (Lymph Nodes)	 Retroperitoneal (including Para/Peri-Aortic R/L and Celiac axis R/L) Supradiaphragmatic (including Supraclavicular R/L, Pre/Paratracheal R/L, Posterior Mediastinal R/L, Anterior Mediastinal R/L, Subcarinal, Paracardiac R/L, Retrocrural R/L, Thoracic Hilar R/L, Mesenteric R/L, Axillary R/L, Cervical R/L)

Statistical Analysis Plan: Protocol PyL3301

Anatomic Region	CLR Lesion Locations
	Other extra-pelvic (specify, including Inguinal/Femoral R/L)
Extra-pelvic (Bone)	 Pelvic bone R/L Skull Clavicle R/L Scapula R/L Sternum Ribcage R/L Spine (including cervical/thoracic/lumbar/sacral) Extremities (including right upper, right lower, left upper, left lower) Other bone lesion
Extra-pelvic (Visceral/soft- tissue)	 Lung/pleura Liver Other visceral/soft tissue lesion (including spleen, adrenal, mediastinum, pericardium, non-nodal retroperitoneal tissue, and other visceral/soft-tissue)

Each subject will be evaluated for the primary endpoint using a single truth standard source. If a subject has more than one source, e.g., undergoes correlative imaging and needle-guided biopsy, the pathology result from the needle biopsy will be evaluated as the truth standard. If the pathology result is unevaluable or the biopsy needle is not in a positive PyL lesion, then the results of the correlative imaging will be used as the truth standard.

Subjects with positive ¹⁸F-DCFPyL PET/CT scans per local scan interpretation (detection of disease at any location) will be followed at the Efficacy visit(s) based on their ¹⁸F-DCFPyL PET/CT finding(s) (see Section 4). If a subject has a negative ¹⁸F-DCFPyL scan by the local interpretation, then no standard of truth data will be submitted by the study site and no efficacy evaluation will be performed by the central Truth Panel readers. If the subject's ¹⁸F-DCFPyL PET/CT scan is interpreted as positive by one or more of the central readers and no standard of truth data is available for evaluation, then the subject will be considered unevaluable for the primary endpoint. Please see Section 5.1.3 for subjects with positive ¹⁸F-DCFPyL scans by local interpretation where the central reader(s) identify the scan as negative.

Subjects with positive ¹⁸F-DCFPyL PET/CT scans (by central review) will be classified as TP, FP or unevaluable as presented in Table 4.

Table 4: Primary Endpoint Assessment

Composite Truth Standard Source	Truth Standard Location Result	Central PyL Reader Location Match	Subject Outcome

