8.5.2.2. Sensitivity Analyses of the Primary Endpoint

The primary endpoint analysis will be repeated for subjects in the per-protocol analysis set, which excludes subjects with major protocol deviations.

There will also be an analysis of the primary endpoint for subjects who have positive ¹⁸F-DCFPyL scans as reported by local interpretation. These subjects will have their endpoint evaluated following the same criteria as described in Table 3. The CLR and its corresponding 95% confidence interval will be calculated in the same manner as for the three independent central PyL readers. If there are more subjects with positive PyL scans identified by the central readers than those identified by the local readers, then a population of subjects with positive scans by local read results may be used.

There will be an analysis of the primary endpoint in the full analysis set with positive ¹⁸F-DCFPyL PET/CT imaging as assessed by the central imaging readers, where the CLR lesion location recorded for pelvic lymph nodes will be grouped according to the PROMISE - standardized lymph node template² (internal iliac left, internal iliac right, external iliac left, internal iliac right, obturator left, obturator right, common iliac left, common iliac right, presacral and other pelvic lymph nodes). All other CLR lesion locations will be assessed, including laterality where applicable, as described in Table 3.

There will be an analysis of the primary endpoint in the full analysis set with positive ¹⁸F-DCFPyL PET/CT imaging as assessed by the central imaging readers, where the specific lesion location recorded on the case report form, including laterality where applicable, is used instead of the CLR lesion location as described in Table 3.

A summary table will present the number and percent of subjects with either false negative or true negative outcomes for each central imaging reader. A data listing of subjects in these endpoint categories will also be prepared.

As noted in section 8.4, pattern mixture model-based multiple imputations (MI) assuming data are missing-at-random (MAR) and tipping point analyses will be performed as sensitivity analyses to examine the influence of the missing or unevaluable SOTs for subjects who have ¹⁸F-DCFPyL PET/CT results reported by a central reader. ¹⁰ The locations of lesions as identified by the central reader(s) will be imputed as the lesion locations in the multiple imputation scenarios.

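### SAP Table 3 files abdominal mesenteric nodes as supradiaphragmatic, so the primary location match can pair them with axillary or cervical lesions; two smaller corrections belong with it

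*SAP*

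**What the plan says.** The primary endpoint in Protocol 3.1 rests on a "one-to-one correspondence between localization of at least one lesion" seen on PyL PET/CT and the composite truth standard. SAP 5.1.1 turns this into a rule: "The CLR lesion location(s) will be matched with the CLR lesion location(s) identified by the composite truth standard to determine if colocalization is successful". The locations are listed in Table 3, and side is handled by the statement that "CLR lesion locations matched by laterality (right or left) where applicable are presented in Table 3". The SAP does not say location by location where side applies.

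Three entries matter here.

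- **Table 3, extra-pelvic lymph nodes.** The supradiaphragmatic location runs "Supradiaphragmatic (including Supraclavicular R/L, Pre/Paratracheal R/L, Posterior Mediastinal R/L, Anterior Mediastinal R/L, Subcarinal, Paracardiac R/L, Retrocrural R/L, Thoracic Hilar R/L, Mesenteric R/L" and continues through the axillary and cervical nodes; its last four entries are "Thoracic Hilar R/L, Mesenteric R/L, Axillary R/L, Cervical R/L". All of these form one location.
- **Table 3, visceral and soft tissue.** The catch-all location is "Other visceral/soft tissue lesion (including spleen, adrenal, mediastinum, pericardium, non-nodal retroperitoneal tissue", followed by any remaining visceral or soft-tissue site.
- **SAP 8.5.2.2, PROMISE sensitivity analysis.** The pelvic node list begins "internal iliac left, internal iliac right, external iliac left, internal iliac right, obturator left, obturator right".

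Table 4 and its note score a match to a positive truth finding as a true positive and a location mismatch as a false positive. For PSA response after RT, location matching is marked as not applicable.

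**The concern.** Table 3 is part of the scoring rule for the primary endpoint, not a display convention. Mesenteric nodes lie below the diaphragm, so the supradiaphragmatic row contradicts its own label. Programmed as written, a mesenteric call by a central reader is correctly localized by an axillary or cervical truth lesion on the same side. That pair cannot be a one-to-one correspondence of location.

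The catch-all visceral row has a similar weakness. A splenic call and a pericardial truth lesion share a location, and laterality does not separate them. SAP 5.1.1 explains the pelvic node grouping (alignment with the PyL-2301 study) and the prostatic and extra-pelvic node groupings (PROMISE). It gives no reason for the visceral pool.

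The PROMISE list leaves right external iliac nodes without a named category, while the left ones have one. A program that follows the list literally treats the two sides differently.

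What is at stake is a false true positive in an endpoint whose success rule can turn on one subject if the observed CLR is near its planning value.

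**Working it through.** **Step 1. Trace a mesenteric call through the rule.**

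| Reader's call | Truth lesion | Table 3 locations | Outcome as written | Outcome with a separate mesenteric location |
|---|---|---|---|---|
| Mesenteric, right | Mesenteric, right | same | TP | TP |
| Mesenteric, right | Axillary or cervical, right | same | TP | FP |
| Mesenteric, right | Para-aortic, right | different | FP | FP |

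Only the second line changes. Splitting a location can remove matches but cannot create them. The same holds for requiring the same organ in the catch-all visceral row. Since a mismatch counts as FP, the denominator TP + FP stays the same and the CLR can only stay or fall.

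**Step 2. Count the PROMISE list.** It has ten entries and nine distinct names: right internal iliac twice, left external iliac once, right external iliac not at all. Table 3 itself places external iliac nodes in both the right and the left pelvic location, so the primary match is unaffected.

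**Step 3. Reproduce the planned size.** Inputs from SAP 7.1: CLR 30%, lower bound 20%, normal approximation, two-sided 95%.

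n = 1.96² × 0.30 × 0.70 / 0.10² = 80.67, rounded up to 81. This agrees with the plan.

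**Step 4. Find the pass mark per reader.** SAP 8.5.2.1 requires a lower bound above 0.2. Lower bound = p − 1.96 × √(p(1 − p)/81).

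- 24 TP: p = 0.2963, SE = 0.0507, lower bound 0.197 (fail).
- 25 TP: p = 0.3086, SE = 0.0513, lower bound 0.208 (success).

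**Step 5. Illustrate the number affected.** The documents give no distribution of verified lesions by location. Assume that 10% to 20% of 81 evaluable subjects are verified in broad extra-pelvic locations, that the 30% CLR applies there, and that one match in ten pairs unrelated sites. Only true positives can be wrongly counted as true positives, so the 10% applies to them.

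- Low: 81 × 0.10 = 8.1 subjects; × 0.30 = 2.43 TP; × 0.10 = 0.24 subject.
- High: 81 × 0.20 = 16.2 subjects; × 0.30 = 4.86 TP; × 0.10 = 0.49 subject.

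**Step 6. Check a higher CLR.** With an observed CLR of 50% and as many as 20% of TPs lost, the CLR is 40%. The lower bound is 0.40 − 1.96 × √(0.40 × 0.60/81) = 0.293, well above 0.2.

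**The case against.** The strongest reply is that false matches of this kind are already hard to produce.

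- The truth finding must be the anatomical correlate of a PyL-suspected lesion, and an image-guided biopsy counts only if the sampling device is shown to be in a PyL-positive lesion. A false match therefore needs a central reader to miss the verified site and to call another site in the same location.
- PSA-verified subjects need no location match.
- Success needs two of three readers, so a change in one reader need not change the result.
- SAP 8.5.2.2 already repeats the primary analysis with the specific CRF location.
- The Imaging Review Charter, which is not among the documents, may restrict matching further.

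All of this stands, and it keeps the effect small. It does not make the mesenteric entry right. The CRF-location analysis does not decide success, and the PROMISE analysis regroups only pelvic nodes, so it keeps the mesenteric entry as it is in Table 3.

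A reader might infer that Table 3 is too coarse in general, for example because the whole spine is one location. The documents do not support calling that an error. It is a choice of granularity, made in advance, and the CRF-location analysis will show its effect. Nor is it a fault that a mesenteric call mismatches a para-aortic lesion: these are different sites and would still mismatch after correction.

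**Conclusion.** The mesenteric entry is an error in the primary matching rule and should be corrected. The iliac entry is almost certainly a typing slip. It affects one sensitivity analysis and never the primary CLR. Where right external iliac nodes would go under the printed list is not stated; the other-pelvic group is a guess. The catch-all visceral row should be tightened because it has no stated reason and can join different organs.

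The effect is probably well under one subject per reader at n = 81 and a CLR of 30%, under the assumed shares in the working. A reader might infer one or two subjects by taking 10% of all 8 to 16 subjects verified in such locations. That overstates it, because those already scored as false positives cannot be false matches. The 24-versus-25 boundary shows why even one subject could matter to a reader's result, but only if the observed CLR is close to 30%. The documents do not show a material threat to the primary result.

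**What to change.** Make these changes in the SAP before database lock.

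1. In Table 3, take the mesenteric nodes out of the supradiaphragmatic location and give them their own abdominal (infradiaphragmatic) location. Do not move them to *Other extra-pelvic*: that row also holds inguinal and femoral nodes, so the same kind of false match would return.
2. In the catch-all visceral and soft-tissue row, count a match only when the reader and the truth standard name the same organ, using the specific location already on the CRF.
3. In SAP 8.5.2.2, change the second right internal iliac entry to right external iliac.
4. Leave spine granularity to the planned CRF-location sensitivity analysis.

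The cost is a table edit, a list correction and an update to the mapping code. No new data are needed. The downside is a possibly slightly lower CLR.
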